5.2 Duration of Investigational Product Exposure

For each subject, the duration of investigational product exposure is defined for a given study period as the date of last dose of study drug during the study period – date of first dose of study drug during the study period + 1.

For each subject, the duration of UX007 exposure is defined for a given study period as the date of last dose of UX007 during the study period – date of first dose of UX007 during the study period + 1.

5.3 Study Day

Study day is calculated as (visit date – date of the first dose of investigational product + 1) if the date is on or after the first dose of investigational product; or (visit date – date of the first dose of investigational product) if the date is prior the first dose of investigational product.

5.4 Dosing Compliance

Number of days during a period is calculated as (end of period date – first dose date + 1) for the titration and treatment periods, and (end of period date – week 8 visit date + 1) for the extension period. Percent of days missed for a period is $100 \times (\text{number of days during the period with dose non-compliance}) / (\text{number of days during the period})$.

5.5 Change from Baseline and Percent Change from Baseline

Generally, for measurements at any timepoint T after baseline, change from baseline is defined as

$$\text{Change from Baseline at } T = \text{Measurement at } T - \text{Measurement at Baseline}$$

Percent change from baseline at T is defined as

$$\begin{aligned} \text{Percent Change from Baseline at } T \\ = 100 \times \frac{\text{Measurement at } T - \text{Measurement at Baseline}}{\text{Measurement at Baseline}} \end{aligned}$$

5.6 Classification of Subjects at Randomization by Seizure Type

Classification of subjects is used to derive the primary efficacy endpoint and to define which subjects are included in secondary endpoint analyses of specific seizure types. At the Randomization Visit, subjects can be classified according to the types of seizures that are recorded on the diary as follows:

- **Observable Seizures Subject:** a subject who meets any of the following:
 - Observable Seizure Frequency (types A, B, C, D, E, F, G, H, I, J, K and L; see Section 5.7.5) greater than or equal to 4 at Randomization
 - Observable Seizure Frequency less than 4 at Randomization and Absence Seizure Frequency less than 4 at Randomization
- **Absence Seizures Subject:** a subject who meets any of the following:
 - has seizure types M, N, O or P (see Section 5.7.5) recorded on the seizure diary during the Baseline Period
 - has absence seizures documented on the Screening EEG
 - Absence Seizure Frequency (see Section 5.7.2) greater than 0 at Randomization

All subjects will either be an Observable Seizures Subject, an Absence Seizures Subject, or both. Since there is potential overlap, the following definitions are used to classify randomized subjects into three mutually exclusive groups:

- **Observable Seizures Only Subject:** a subject who is an Observable Seizures Subject *but not an Absence Seizure Subject*
- **Absence Seizures Only Subject:** a subject who is an Absence Seizures Subject *but not an Observable Seizure Subject*
- **Both Seizures Subject:** a subject who is both an Observable Seizures Subject and an Absence Seizure Subject

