### 7.3.1 Inclusion Criteria

Individuals eligible to participate in this study must meet all of the following criteria:

- 1) Diagnosis of Glut1 DS confirmed by *SLC2A1* mutation
- 2) Males and females at least 1 year of age at the time of informed consent
- 3) Average of at least 2 observable seizures (generalized or partial-onset [simple partial motor, complex partial, absence, or secondarily generalized] seizures) in 4 weeks over the last 24 weeks, by subject or caregiver report
- 4) At least 2 observable seizures (generalized or partial-onset [simple partial motor, complex partial, or secondarily generalized] seizures) in 4 weeks during the baseline period, with no 3-week seizure-free period during the Baseline Period OR absence seizures documented on Screening EEG
- 5) Continuing to have seizures despite a prior or current use of at least 1 AED
- 6) Allowed to be on up to 3 concomitant AEDs that must have been stable in dose at least 2 weeks prior to the beginning of screening and anticipated to remain stable in dose through the end of the 8-week, placebo-controlled Treatment Period
- 7) Not on, or not fully compliant with a prescribed diet plan (e.g. KD)
- 8) Plasma level of beta-hydroxybutyrate (BHB)  $\leq 1$  mmol/L (non-fasting) at Screening
- 9) Provide written or verbal assent (if possible) and written informed consent by a legally authorized representative after the nature of the study has been explained, and prior to any research-related procedures
- 10) Must, in the opinion of the investigator, be willing and able to complete all aspects of the study, comply with accurate completion of the seizures diary, and likely to complete the 8-week, placebo-controlled, Treatment Period
- 11) Females of childbearing potential must have a negative pregnancy test at Screening, be willing to use an acceptable method of contraception, and have additional

pregnancy tests during the study. Females considered not of childbearing potential include those who have not reached menarche, had total hysterectomy, have been in menopause for at least two years, or have had tubal ligation at least one year prior to Screening.

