4.1 Primary Efficacy Endpoint

The primary endpoint to evaluate the efficacy of UX007 in Glut1 DS is as follows:

- Reduction from baseline to week 8 in frequency of seizures (normalized to a 4-week rate): observable seizures measured for 6 weeks after 2-week titration by diary and absence seizures measured overnight by electroencephalography (EEG). The primary efficacy endpoint will be derived for each subject based on subject seizure type at randomization: observable seizures from the diary will be used for Observable Seizures Subjects and absence seizures from EEG will be used for Absence Seizures Only Subjects (see Section 5.6).

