5.7 Derived Seizure Efficacy Variables

5.7.1 Observable Seizure Frequency

Observable seizure frequency, the observable non-absence seizure frequency from the diary (normalized to a 4-week rate), is defined as

$$\text{Observable Seizure Frequency} = \frac{\text{Total number of seizures}}{\text{Number of days observed}} \times 28$$

See Section 5.7.5 for the list of observable seizure types that are counted. For analyses, observable seizure frequency will be defined at each of the following timepoints as follows:

- Baseline: approximately 6 weeks between the day of the screening visit and the day prior to the randomization visit
- End of Titration: approximately 2 weeks between the day of the randomization visit and the day prior to the end of titration visit
- Week 8: approximately 6 weeks between the day of the end of titration visit and the day prior to the week 8 visit

If a subject misses a visit, then the expected visit date will be used in place of the actual visit date to define observable seizure frequency. Expected visit date is the date of the previous visit + the expected number of weeks between the previous visit and the missing visit. If the previous visit is also missing, then the expected date of the previous visit would be used instead.

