5.7.2 Absence Seizure Frequency

The absence seizure frequency from EEG (normalized to a 24-hour rate) is defined as

$$\text{Absence Seizure Frequency} = \frac{\text{Total number of absence seizures}}{\text{Number of hours observed}} \times 24$$

See Section 5.7.6 for the list of absence seizure types that are counted. Absence seizure frequency at baseline is measured at the randomization visit. Absence seizure frequency at 8 weeks is measured at the week 8 visit (Visit 5).

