5.7.3 Percent Reduction from Baseline in Seizure Frequency

For observable or absence seizures, the percent reduction from baseline in seizure frequency during a period T is defined as

$$\text{Percent Reduction from Baseline} = 100 \times \frac{\text{Frequency at Baseline} - \text{Frequency at } T}{\text{Frequency at Baseline}}$$

The maximum percent reduction is 100% and occurs when the frequency is reduced to zero. If the frequency increases then the percent reduction is a negative number.

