8.6.3 Primary Efficacy Endpoint

The primary efficacy endpoint is the reduction from baseline to week 8 in frequency of seizures (normalized to a 4-week rate): observable seizures measured for 6 weeks after 2-week titration by diary and absence seizures measured overnight by electroencephalography (EEG). Observable seizure frequency at baseline will be calculated based on approximately 6 weeks between the screening and randomization visits and observable seizure frequency at week 8 will be calculated based on approximately 6 weeks between the end of titration and the week 8 visit (see Section 5.7.1). Absence seizure frequency will be based on overnight EEG at the randomization and week 8 visits.

The primary efficacy endpoint will be derived for each subject based on subject seizure type at randomization: observable seizures from the diary will be used for Observable Seizures Subjects and absence seizures from EEG will be used for Absence Seizures Only Subjects (see Section 5.6).

The primary efficacy endpoint will be analyzed, based on the Efficacy Analysis Set, using a linear regression (ANCOVA) model as described for continuous endpoints in Section 8.6.1. Logarithmic transformations will be used for modeling. The response variable in the model will be the reduction in the natural logarithm of the seizure frequency (+ 1) from baseline to Week 8 and the baseline covariate will be the natural logarithm of the baseline seizure frequency (+ 1): observable seizures from the diary will be used for Observable Seizures Subjects and absence seizures from EEG will be used for Absence Seizures Only Subjects.

An additional covariate will be included that indicates whether the subject is an Observable Seizures Subject or an Absence Seizures Only Subject. Estimates and 90% confidence intervals of percent reduction in seizure frequency will be derived from the model for each treatment group and for the difference between groups.

Missing data will be imputed as specified in Section 7.1. Sensitivity analysis assessing the impact of missing data will be performed using the methods described in Section 7.1.

Percent reduction from baseline in frequency of seizures over the entire study period will be summarized by visit (see Section 5.7.1), and by treatment group, for subjects while taking UX007, and overall.

The following additional analyses will be performed:

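### SAP 5.6's catch-all rule has no lower bound, so some patients enrolled on absence seizures are scored in the primary analysis on a diary baseline of zero

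*SAP*

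**What the plan says.** **Entry.** Inclusion criterion 4 (Protocol 7.3.1) asks for at least 2 observable seizures in 4 weeks of baseline, with no 3-week gap, "OR absence seizures documented on Screening EEG". The second route has no diary minimum. Criterion 3 also accepts absence seizures in the 24-week history.

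**Classification.** SAP 5.6 gives two ways to be an Observable Seizures Subject: observable frequency of 4 or more, or "Observable Seizure Frequency less than 4 at Randomization and Absence Seizure Frequency less than 4 at Randomization". An Absence Seizures Only Subject is one who is in the absence class and not in the observable class. Anyone caught by the catch-all therefore cannot be Absence Seizures Only.

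**Data source.** For the primary endpoint (SAP 4.1, repeated in 8.6.3), "observable seizures from the diary will be used for Observable Seizures Subjects". EEG is used only for Absence Seizures Only Subjects. The diary frequency (SAP 5.7.1, Table 2) leaves out the absence codes M to P.

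**Scoring.** The modelled response is the "reduction in the natural logarithm of the seizure frequency (+ 1) from baseline to Week 8" (SAP 8.6.3). Percent reduction (SAP 5.7.3) divides by baseline frequency: "The maximum percent reduction is 100% and occurs when the frequency is reduced to zero". Response (SAP 5.7.4) is a percent reduction of at least 50%. SAP 7.1 has rules for missing data but none for a baseline of zero.

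**The concern.** Amendment 3 opened the trial to patients who have only absence seizures. Such a patient can have a diary baseline of exactly zero. If the Week 0 EEG also shows few events, the catch-all sends that patient to the diary, the one measure on which no improvement can be recorded. The best attainable score, 0, is the value SAP 7.1 imputes for a subject with completely missing data.

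The rule also sorts patients in an odd order. A patient with 2 observable seizures per 4 weeks and 6 absence seizures per 24 hours has a usable diary baseline and goes to EEG. A patient with 0 and 2 has no diary baseline and goes to the diary. SAP 6.3.4 notes that the Absence Seizures Only set includes some subjects with fewer than 4 observable seizures, so the SAP does intend some low-diary absence patients to be scored on EEG.

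Nothing in the primary model would flag the problem. Adding 1 before taking logs lets the ANCOVA run, and the Observable/Absence Only covariate labels these subjects Observable. At stake are the primary estimate and the definition of the 50% response.

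**Working it through.** **1. The plan's own power figure.** SAP 3.5: difference 50, SD 55, about 40 subjects, one-sided 0.05; SAP 3.3: 3:1 allocation, so 30 and 10. SE = 55 × √(1/30 + 1/10) = 20.08; 50/20.08 − 1.645 = 0.845, giving 80.1% power. The exact t calculation gives 78.8%. The stated figure of approximately 80% is reproduced.

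**2. Who is caught.** SAP 5.7.2 sets the absence rate: "The absence seizure frequency from EEG (normalized to a 24-hour rate) is defined as" events divided by hours observed, times 24. On the 12-hour minimum recording (Protocol 7.5.2.1), 1 event gives 1/12 × 24 = 2 and 2 events give 4. So below 4 means 0 or 1 event. For patients with absence seizures on the Screening EEG:

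| Diary per 4 weeks | EEG per 24 h | Class | Primary source |
|---|---|---|---|
| 0 | 0 | Both | diary |
| 0 | 2 | Both | diary |
| 0 | 4 or 40 | Absence Only | EEG |
| 2 | 6 | Absence Only | EEG |

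**3. What they score.** With diary baseline 0, the response is ln(0 + 1) − ln(W8 + 1) = −ln(W8 + 1). It is 0 if Week 8 is 0. One seizure in 42 days is 28/42 = 0.67 per 4 weeks and scores −ln(1.67) = −0.51. On EEG, a fall from 2 to 0 per 24 hours would score ln 3 = +1.10. Percent reduction has 0 in the denominator.

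**4. Scale.** SAP 4.1 and 4.2 describe the absence rate as normalized to 4 weeks. On that scale one event in 12 hours is 1/12 × 24 × 28 = 56, so only a zero EEG count would be caught.

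**5. How often (Poisson counts assumed).** At a true rate of 4 per 24 hours, P(0 or 1 event in 12 h) = 41%. Entry through a Screening EEG of about 3 hours also needs at least one event there: 1 − e^(−0.5) = 39%. Both together: 0.39 × 0.41 = 16%, before requiring a zero diary. At 8 per 24 hours: 0.63 × 0.092 = 5.8%.

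**6. Size.** If k of 40 subjects contribute no effect, evenly over arms, a true log difference of ln 2 = 0.693 becomes 0.693 × (1 − k/40): 0.658, 0.624 and 0.589 for k = 2, 4, 6. A simulated ANCOVA (30 against 10, residual SD 0.75 on the log scale, affected subjects set to baseline 0 and response 0, 4,000 runs) gave 0.69, 0.66, 0.63 and 0.60 for k = 0, 2, 4, 6, with power 79%, 77%, 74% and 73%. On the SAP's percent scale with SD held at 55, power is 80.1%, 76.4% and 72.4% for k = 0, 2, 4. Neither k nor the SD of 0.75 is in the documents.

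**7. Does EEG scoring help?** The simulation was repeated with affected subjects scored on a 12-hour EEG, Poisson counts, rate 4 or 8 per 24 hours and halved by drug. With 6 of 40 affected, the mean estimate rose from 0.59 to 0.68–0.69. Power moved only between about 2 points down and 4 points up. Of those caught on a 12-hour EEG, 1/(1 + 2) = 33% at rate 4 and 1/(1 + 4) = 20% at rate 8 have no event at all, so their EEG baseline is also zero.

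**The case against.** The reach is narrow. The patient must enter through the short Screening EEG, record none of twelve observable seizure types over about six weeks, and then show at most one event on an overnight EEG that also counts indeterminate events of 3 to 10 seconds (SAP Table 3). The catch-all has a purpose: without it, a subject with few observable and no absence seizures would belong to no class. The bias runs toward no effect. Protocol 7.3 also says that only subjects with at least 2 observable seizures per 4 weeks will be randomized, which would rule the case out.

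Most of this stands as a limit on weight. The Protocol 7.3 sentence does not settle the matter, because it contradicts inclusion criterion 4 and, read literally, would bar the absence-only patients whom Amendment 3 admitted.

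Four stronger readings are tempting and not supported:

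- A reader might infer that absence patients in general are kept off EEG. Those at 4 or more per 24 hours, with fewer than 4 observable seizures per 4 weeks, are scored on EEG as intended.
- A reader might infer that the EEG data are discarded. These patients are scored on EEG in the secondary absence endpoints (SAP 8.6.4), the fallback absence test and the alternative derivation of the primary (both SAP 8.6.3). Only the primary itself, and the response analysis built the same way, use the diary.
- A reader might infer that no treatment difference can arise among them. The ceiling is on the individual score; the contrast can still move if placebo subjects worsen from zero.
- A reader might take the 41% as the share of absence patients affected. It applies only at a true rate exactly on the cut-off and ignores the Screening EEG requirement.

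**Conclusion.** The point holds as a drafting gap in a stated rule. A documented-absence patient with a zero diary and fewer than 4 absence seizures per 24 hours at Week 0 gets a primary response that cannot exceed 0 and a 50% response that is undefined. The planned EEG-based analyses do not repair the primary.

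The consequence is dilution of the primary estimate, from 0.69 to about 0.66, 0.63 and 0.60 with 2, 4 and 6 of 40 affected. Power falls by roughly 2 to 4 points with two affected and 5 to 8 with four, depending on the method. These figures rest on an assumed effect of ln 2, an assumed log-scale SD of 0.75 (or the SAP's 55 on the percent scale) and assumed numbers of affected subjects. The true number is not in the documents and may be small or zero. The reach also depends on the 24-hour scale of SAP 5.7.2.

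This should be fixed before unblinding. The documents do not support calling it a flaw that invalidates the primary analysis.

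**What to change.** Before unblinding:

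1. In SAP 5.6, change the second Observable condition to an observable frequency above 0 and below 4, with absence frequency below 4. Absence Seizures Subjects with an observable frequency of 0 then become Absence Seizures Only and are scored on EEG in the primary and response analyses.
2. Keep a fallback to the Observable class for any subject with no documented absence seizures, so that every subject is still classified.
3. State a rule for a zero baseline on the selected measure. For example: count the subject as a non-responder, keep the ln(f + 1) value in the ANCOVA, and add a sensitivity analysis that excludes subjects with a zero baseline.
4. Reconcile the absence scale between SAP 4.1 and 4.2 (4-week) and 5.7.2 (24-hour). If the 4-week scale is meant, every patient caught has a zero EEG count, and only the rule in item 3 helps.
5. Reconcile Protocol 7.3 with inclusion criterion 4 on whether such patients are randomized.

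The cost is a few sentences in the SAP and a re-run of the classification. The downside is that the moved subjects have low, noisy and quite often zero EEG baselines, so the gain is mainly less bias rather than more power.

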5.7 Derived Seizure Efficacy Variables

5.7.1 Observable Seizure Frequency

Observable seizure frequency, the observable non-absence seizure frequency from the diary (normalized to a 4-week rate), is defined as

$$\text{Observable Seizure Frequency} = \frac{\text{Total number of seizures}}{\text{Number of days observed}} \times 28$$

See Section 5.7.5 for the list of observable seizure types that are counted. For analyses, observable seizure frequency will be defined at each of the following timepoints as follows:

- Baseline: approximately 6 weeks between the day of the screening visit and the day prior to the randomization visit
- End of Titration: approximately 2 weeks between the day of the randomization visit and the day prior to the end of titration visit
- Week 8: approximately 6 weeks between the day of the end of titration visit and the day prior to the week 8 visit

If a subject misses a visit, then the expected visit date will be used in place of the actual visit date to define observable seizure frequency. Expected visit date is the date of the previous visit + the expected number of weeks between the previous visit and the missing visit. If the previous visit is also missing, then the expected date of the previous visit would be used instead.

5.7.2 Absence Seizure Frequency

The absence seizure frequency from EEG (normalized to a 24-hour rate) is defined as

$$\text{Absence Seizure Frequency} = \frac{\text{Total number of absence seizures}}{\text{Number of hours observed}} \times 24$$

See Section 5.7.6 for the list of absence seizure types that are counted. Absence seizure frequency at baseline is measured at the randomization visit. Absence seizure frequency at 8 weeks is measured at the week 8 visit (Visit 5).

5.7.3 Percent Reduction from Baseline in Seizure Frequency

For observable or absence seizures, the percent reduction from baseline in seizure frequency during a period T is defined as

$$\text{Percent Reduction from Baseline} = 100 \times \frac{\text{Frequency at Baseline} - \text{Frequency at } T}{\text{Frequency at Baseline}}$$

The maximum percent reduction is 100% and occurs when the frequency is reduced to zero. If the frequency increases then the percent reduction is a negative number.

5.7.4 Seizure Response

Seizure response is defined as a percent reduction from baseline in seizure frequency greater than or equal to 50%.

Observable seizure response, at least 50% reduction from baseline in frequency of observable seizures measured by diary, is defined as percent reduction in observable seizure frequency greater than or equal to 50%.

Absence seizure response, at least 50% reduction from baseline in frequency of absence seizures measured overnight by EEG, is defined as percent reduction in absence seizure frequency greater than or equal to 50%.

5.7.5 Classification of Seizures from Diary

Table 2 shows the seizure classifications that are distinguished in the seizure diary, and which are counted towards study inclusion criteria and when deriving the observable seizures endpoints.

Table 2: Seizure Classification by Diary

Seizure Code (Diary)	Seizure Classification	Counted Towards Inclusion Criteria	Counted as Observable Seizure
A	Generalized Tonic-Clonic	X	X
B	Generalized Tonic	X	X
C	Generalized Clonic	X	X
D	Generalized Atonic	X	X
E	Partial/Focal with Secondary Generalization	X	X
F	Myoclonic	X	X
G	Myoclonic (Astatic) Atonic	X	X
H	Myoclonic Tonic	X	X
I	Complex Partial/Focal	X	X
J	Simple Partial/Focal Motor	X	X
K	Simple Partial/Focal Sensory		X
L	Simple Partial/Focal Psychological		X
M	Typical Absence	X [*]	
N	Atypical Absence	X [*]	
O	Absence with Special Features (Myoclonic absence)	X [*]	
P	Absence with Special Features (Eyelid myoclonia)	X [*]	

Seizure Code (Diary)	Seizure Classification	Counted Towards Inclusion Criteria	Counted as Observable Seizure
Q	Unclassified (Inc. epileptic spasms)		
UNK	Unknown		

[*] Note that for the first 3 subjects PPD subjects, seizure codes MNOP were not counted towards study inclusion criteria because they were randomized prior to the implementation of Protocol Amendment 3.

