### **5.5 Primary Efficacy Hypothesis**

UX007 is more effective than placebo for the reduction of seizures in patients with Glut1 DS, as measured by the reduction from randomization in frequency of seizures, including: Generalized Tonic-Clonic, Generalized Tonic, Generalized Clonic, Generalized Atonic, Partial/Focal with Secondary Generalization, Myoclonic, Myoclonic Atonic, Myoclonic Tonic, Complex Partial/Focal, Absence, and Simple Partial/Focal Motor seizures.

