### 7.5.2.1 Primary Efficacy Variable

**Seizure Frequency Reduction:** Percent reduction from randomization to week 8 in frequency of seizures. Observable generalized and partial-onset seizures measured for 6 weeks by diary and absence seizures measured overnight by electroencephalography (EEG).

Seizures are a hallmark of Glut1 DS in approximately 90% of affected individuals ([Wang et al. 2012](#)). The frequency of seizures varies among individuals; some experience daily events while others may have seizures separated by days, weeks, or even months. The number of observable seizures will be recorded by the subject or caregiver via diary throughout the study.

The frequency of different seizure types will be recorded. Seizure types will be defined and standardized according to the ILAE Commission on Classification and Terminology ([Berg et al. 2010](#)). Indicated seizure types are consistent with those observed in a large Glut1 DS cohort study designed to define epilepsy phenotypes in this population ([Pong et al. 2012](#)).

Observable seizures for the primary efficacy measure are defined as:

- Generalized Tonic-Clonic, Generalized Tonic, Generalized Clonic, Generalized Atonic
- Partial/Focal with Secondary Generalization
- Myoclonic, Myoclonic (Astatic) Atonic, Myoclonic Tonic
- Complex Partial/Focal
- Simple Partial/Focal Motor

**Electroencephalography:** Case-report studies in limited groups of Glut1 DS patients suggest a normal interictal background is the most common finding on both routine and prolonged EEG recordings. Both absence and myoclonic seizures have been observed in pediatric Glut1 DS patients during overnight continuous monitoring ([Leary et al. 2003](#)).

Several studies have examined electrophysiologic characteristics in Glut1 DS patients on KDs (Kessler et al. 2011).

Abnormalities on EEG (including absence seizures) will be recorded with an overnight EEG conducted at the Week 0, 8, 26, and 31 visits. Confirmatory EEG at Screening for patients with absence seizures only is required for ~3 hours. For Week 0 EEG, begin EEG PRIOR TO Randomization date. Monitoring periods of less than 12 hours in duration for Week 0, 8, 26, and 31 visits will be considered a protocol violation. Key measures will include: (1) frequency of EEG seizures, including absence; and (2) frequency of interictal epileptiform discharges.

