### **7.6.3 Primary Efficacy Analysis**

The primary efficacy analysis will be based on the efficacy analysis set. The UX007 treatment group will be compared with placebo. The primary efficacy evaluation is the percent reduction from randomization to week 8 in frequency, normalized to a 4 week rate, of seizures. Observable generalized and partial-onset seizures measured for 6 weeks by diary and absence seizures measured overnight by electroencephalography (EEG). Seizure types include: Generalized Tonic-Clonic, Generalized Tonic, Generalized Clonic, Generalized Atonic, Partial/Focal with Secondary Generalization, Myoclonic, Myoclonic Atonic, Myoclonic Tonic, Complex Partial/Focal, Simple Partial/Focal Motor and Absence seizures. Summaries using descriptive statistics: n, mean, SE, median, minimum and maximum will be provided. The primary efficacy comparison will be made using an appropriate analysis as defined in the SAP.

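### The SAP counts simple partial sensory (K) and psychological (L) seizures in the primary diary frequency and in the diary-or-EEG cut-off, although the protocol's definition of observable seizures stops at simple partial motor

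*SAP*

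**What the plan says.** Protocol Section 7.5.2.1 introduces its list with "Observable seizures for the primary efficacy measure are defined as". The list has ten types, which correspond to diary codes A to J, and ends at "Simple Partial/Focal Motor". The primary hypothesis (Section 5.5) and the primary analysis (Section 7.6.3) name the same ten types plus absence; their lists close with "Complex Partial/Focal, Absence, and Simple Partial/Focal Motor seizures" and "Complex Partial/Focal, Simple Partial/Focal Motor and Absence seizures" respectively. None of these places names a sensory or psychological type.

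SAP Table 2 (Section 5.7.5) marks twelve codes as observable: A to J, K ("Simple Partial/Focal Sensory") and L ("Simple Partial/Focal Psychological"). Section 5.7.1 makes that table govern the frequency: "See Section 5.7.5 for the list of observable seizure types that are counted". Section 5.6 repeats the wider set in the classification rule: "Observable Seizure Frequency (types A, B, C, D, E, F, G, H, I, J, K and L", with a threshold of at least 4. Sections 4.1 and 8.6.3 then take the primary endpoint from the diary for Observable Seizures Subjects and from the EEG for Absence Seizures Only Subjects.

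**The concern.** The SAP widens the primary diary count from ten seizure types to twelve without explanation. Its introduction says that it gives the detail of analyses outlined in the protocol, so a reader would expect either the protocol's list or a stated reason for leaving it.

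The same count is used in several places: the primary response, its baseline covariate, the observable-seizure reduction and response endpoints, the overall responder endpoint, and the indicator covariate that separates Observable Seizures Subjects from Absence Seizures Only Subjects. Two analysts, one working from the protocol and one from the SAP, could derive different primary values for the same subject, and in some cases would take them from different instruments.

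**Working it through.** **Sample size.** The plan's power figure reproduces and is not affected. Inputs (Protocol 7.4.3 and 7.6.9): 40 subjects at 3:1, so 30 and 10; difference 50; SD 55; one-sided alpha 0.05. Normal approximation: 50 / (55 × √(1/10 + 1/30)) = 2.49; 2.49 − 1.645 = 0.845; power 80.1%. The noncentral t gives 78.8%. The plan states about 80%. No seizure-type list enters this calculation.

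**The definitions side by side.**

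| Place | Simple partial types covered | Diary codes |
|---|---|---|
| Protocol 7.5.2.1 (definition) | motor | A-J |
| Protocol 5.5 and 7.6.3 | motor | A-J plus absence |
| SAP Table 2, observable column | motor, sensory, psychological | A-L |
| SAP 5.6, cut-off of 4 | motor, sensory, psychological | A-L |

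**When the data source switches.** Under SAP 5.6 a subject is an Observable Seizures Subject if the observable frequency is at least 4, or if both the observable and the absence frequency are below 4.

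- A-J at least 4: diary, with or without K/L.
- A-J below 4 and absence below 4: diary, with or without K/L.
- A-J below 4, A-L at least 4 and absence at least 4: diary with K/L counted, EEG without.

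So counting K/L can move a subject only from EEG to diary, and only in the third case. Example with assumed values: A-J = 2, K/L = 2, EEG absence = 20 per 24 h.

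- SAP: 2 + 2 = 4, which meets the cut-off, so diary.
- Protocol list: 2 < 4 and 20 ≥ 4, so Absence Seizures Only, and EEG.

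**Effect on the value when the source stays the diary.** Let s be the K/L share of the baseline A-L count. Then

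A-L reduction = (1 − s) × (A-J reduction) + s × (K/L reduction).

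The documents give no K/L frequencies, so s is assumed over a range. Take A-J at 8 per 4 weeks, falling to 4 (a 50% reduction, which is a response under SAP 5.7.4), with K/L unchanged. K/L at baseline is 8s/(1 − s).

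| s | Baseline A-L | Week 8 A-L | Reduction | Reduction in ln(frequency + 1) |
|---|---|---|---|---|
| 0 | 8.00 | 4.00 | 50% | ln(9/5) = 0.588 |
| 10% | 8.89 | 4.89 | 45% | ln(9.89/5.89) = 0.518 |
| 25% | 10.67 | 6.67 | 37.5% | ln(11.67/7.67) = 0.420 |
| 50% | 16.00 | 12.00 | 25% | ln(17/13) = 0.268 |

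At any share above zero this subject changes from responder to non-responder. The sign depends on the assumption: if K/L seizures instead stopped entirely at s = 25%, the A-L reduction would be 0.75 × 50 + 0.25 × 100 = 62.5%, above the A-J value.

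**Planned analyses that bear on this.** SAP 8.6.3 includes an alternate derivation that uses EEG for every Absence Seizures Subject, and 8.6.4 does the same for seizure response. Anyone in the third case above has EEG absence of at least 4 and is therefore an Absence Seizures Subject, so these analyses use EEG for that person whatever the K/L count. They also move every subject with both seizure types to EEG, so they do not isolate the K/L question, and K/L still count for Observable Seizures Only Subjects. Appendix A lists separate exploratory summaries of sensory and psychological seizures. The remaining additional analyses (multiplicity, inclusion of titration, per protocol, imputation) all keep A-L.

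**The case against.** The best defence is that the protocol is less closed than Section 7.5.2.1 alone suggests. No sentence names sensory or psychological seizures as excluded. The lists in Sections 5.5 and 7.6.3 are introduced as inclusions. The primary objective speaks of generalized and partial-onset seizures, and K and L are partial by name. The Amendment 4 summary describes the intent as covering all seizure types. On that reading the SAP resolves an ambiguity. This explains how K and L may have come in, but Section 7.5.2.1 is the one place that defines the term for the primary measure, and looser wording elsewhere does not displace it. If the SAP meant to resolve an ambiguity, it should say so.

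Second, Table 2 keeps eligibility and endpoint in separate columns, and these also differ for the absence codes M to P. This stands: the fact that K and L do not count towards inclusion is not itself an error, and the point does not rest on it.

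Third, the alternate-source analyses and the K/L summaries make part of the effect visible. This also stands, within the limits shown above.

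A reader might also infer that K and L add noise because caregivers find them hard to record. Neither document says so, and if such seizures were seldom recorded their effect on the count would be small. The point does not need that argument.

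**Conclusion.** The inconsistency is real and sits in the primary endpoint: ten diary codes in the protocol's definition, twelve in the SAP, no reason given, and no planned analysis on the protocol's ten. It reaches both the value of the diary count and, for subjects with A-J below 4, A-L at least 4 and EEG absence at least 4, the choice of instrument.

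Its size is unknown. Only subjects who record K or L are affected, and the documents give no frequency for either. The numerical illustrations rest on assumed rates and shares. A reader might infer that the wider count biases the comparison, or that it invalidates the primary analysis. The documents support neither: the direction depends on how K/L respond relative to A-J, and sample size, power and alpha are unchanged. A reader might also infer that subjects will be moved to the diary on K/L entries alone. The rules allow it, but nothing shows that any subject has that profile. This should be reconciled before the analysis; it does not by itself undermine the trial.

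**What to change.** Before unblinding, do one of the following.

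- Align SAP Section 5.6 and Table 2 with Protocol 7.5.2.1: use A-J for subject classification, the primary endpoint and the observable-seizure endpoints, and report A-L as a sensitivity analysis.
- If K and L are to stay, record this in the SAP as a departure from the protocol with its justification. Add an A-J sensitivity analysis that re-derives both the classification and the endpoint; re-deriving only the count would leave the source switch in place.

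Either way, report by arm how many subjects record K or L and how many change data source. The cost is a short SAP revision, a small change in the derivation and one additional run of the existing models. No new data are needed, because the diary already codes K and L separately.
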